8.2.1.3. Subjects Lost to Follow-up

A subject will be considered lost to follow-up if he or she repeatedly fails to return for scheduled visits and is unable to be contacted by the study site. Site personnel are expected to make diligent attempts to contact subjects who fail to return for a scheduled visit or were otherwise unable to be followed up by the site.

8.2.2. Discontinuation of Study Sites

Study site participation may be discontinued if Lilly, the investigator, or the ERB of the study site judges it necessary for any reason consistent with applicable laws, regulations, and GCP.

8.2.3. Discontinuation of the Study

The study will be discontinued if Lilly judges it necessary for medical, safety, regulatory, or other reasons consistent with applicable laws, regulations, and GCP.

9. Treatment

9.1. Treatment Materials and Supplies

This study involves a comparison of a 100-U bolus of U-500R administered by single SC injection versus administration via CSII and evaluation of U-500R administered SC TID and BID. [Table IBHG.9.1](#) shows the treatment regimens.

Table IBHG.9.1. Investigational Product Regimens

Regimen	Dose	Administration route	Time of administration
Part A	U-500R SC bolus	100-U	Single SC injection Prior to initiation of euglycemic clamp
	U-500R basal infusion plus U-500R CSII bolus	4.25 U/h basal and 100-U bolus	CSII 12 hour infusion of 4.25 U/h U-500R prior to 100-U bolus dose and initiation of euglycemic clamp (with continued 4.25-U/h U-500R infusion)
	U-500R TID	Per titration algorithm (TID, injectable solution)	Multiple daily SC injection Recommended 07:00, 12:00, and 18:00 hours, approximately 30 minutes prior to morning meal, midday meal, and evening meal, respectively ^a
Part B	U-500R BID	Per titration algorithm (BID, injectable solution)	Multiple daily SC injection Recommended 07:00 and 18:00 hours, approximately 30 minutes prior to morning meal and evening meal, respectively ^a

Abbreviations: BID = twice daily; CSII = continuous subcutaneous insulin infusion; SC = subcutaneous;

TID = thrice daily; U-500R = human regular U-500 insulin.

^a If a meal is skipped, insulin dose should be reduced by 50%.

9.2. Treatment Administration

The investigator or designee is responsible for:

- explaining the correct use of the investigational product to the subjects and site personnel,
- verifying that instructions are followed properly,

- maintaining accurate records of investigational product dispensing and collection,
- and returning all unused medication to Lilly or its designee at the end of the study.

Note: In some cases, sites may destroy the material if, during the investigator site selection, the evaluator has verified and documented that the site has appropriate facilities and written procedures to dispose clinical trial materials.

Subjects will be instructed to contact the investigator as soon as possible if he or she has a complaint or problem with the investigational product or drug delivery system so that the situation can be assessed.

All clinical trial material provided to the investigator will be stored in a secure place and allocated and dispensed by appropriately trained persons. The allocation and dispensing of the investigational products will be fully documented and verified by a second person. Detailed records of the amounts of the investigational product received, dispensed, and remaining at the end of the study will be maintained. Not in-use or unopened Humulin R U-500 vials should be stored in a refrigerator, (2°C to 8°C [36° F to 46°F]), but not in the freezer. Once opened, the U-500R vial can be kept unrefrigerated as long as it is kept as cool as possible (below 30°C [86°F]) and away from heat and light. In-use vials must be used within 40 days, even if they still contain U-500R (Humulin R U-500 Package Insert, 2014). Clinical trial materials will be labeled according to the respective country's regulatory requirements.

During periods of prestudy U-100, U-200, and/or U-300 insulin treatment, subjects will self-administer their insulin at home, at approximately the same time each day. The last dose prior to assessment should be taken at approximately the same time in each period and will be at least 15 hours before the U-500R bolus dose and clamp procedure in Part A. The insulin TDD should remain approximately the same throughout Part A of the study (except while subjects are resident in the CRU when it will not be taken).

The insulin preparation will be allowed to come to approximately room temperature prior to administration. The qualified site personnel will be instructed on proper preparation and administration techniques for all insulin used in this study. All insulin will be administered by an appropriately qualified member of the CRU staff while the subject is resident in the CRU.

All SC insulin injections will be given by means of a conventional U-100 insulin syringe (6 mm, 31-gauge needle; 0.5 or 1.0 mL). The same brand and model of syringe will be used throughout the study. The needle will be applied at approximately 90 degrees into a raised skin fold to ensure consistent SC administration. The injection site will be alternated between the 4 quadrants of the abdominal wall, approximately 10 cm from the umbilicus.

In Part A, 100 U of U-500R will be administered by single SC injection or CSII according to the randomization schedule.

For CSII administration, U-500R will be administered via a U-500 OmniPod (currently not available commercially), which will be fitted by qualified staff upon subjects' admission to the CRU. The device will be programmed by CRU staff to administer a 12-hour 4.25-U/h infusion

of U-500R, prior to the 100-U bolus and to continue the 4.25-U/h infusion throughout the clamp procedure. The insulin-on-board function on the U-500 OmniPod will be set at 6 hours. The Pod will be filled from the 20-mL vial of U-500R using only the syringe and needle provided with the U-500 OmniPod by the vendor.

The unit markings on a U-100 insulin syringe do not accurately reflect the unit dose of U-500R because U-500R is 5-times more concentrated than U-100 insulin, and thus only 1/5 the volume is needed to give an equivalent dose to U-100 insulin.

In Part A, for subjects randomized to SC administration, a qualified member of CRU staff will administer 100 U of U-500R, equivalent to 20 unit markings on a 0.5-mL U-100 syringe.

In Part B, CRU staff should instruct subjects on the dose conversion of calculated U-500R to the U-100 syringe unit markings (detailed instruction for which will be provided separately to the site).

All U-500R doses \leq 250 U should be administered using 0.5-mL U-100 insulin syringes. All U-500R doses $>$ 250 U should be administered using 1.0-mL U-100 insulin syringes.

For example:

- 155 U of U-500R have a volume equivalent to 31 U markings on a 0.5 mL U-100 syringe (155 divided by 5=31).
- 100 U of U-500R have a volume equivalent to 20 U markings on a 0.5 mL U-100 syringe (100 divided by 5=20).
- 300 U of U-500R have a volume equivalent to 60 U markings on a 1.0 mL U-100 syringe (300 divided by 5=60).

In Part B, U-500R doses determined as described in Section 9.4 will be administered either TID or BID according to the randomization schedule. The doses will be administered at approximately the same times on each day. The actual time of all dose administrations will be recorded in the subject's eCRF.

9.3. Rationale for Selection of Dose

A dose of 100 U of U-500R was chosen for Part A of this study as this is within the range commonly encountered in high-dose insulin-treated patients whose T2DM is managed with U-500R either by MDI or off-label via CSII (Lane et al. 2009; de la Peña et al. 2011; Reutrakul et al. 2012; Cochran et al. 2014; and Lane et al. 2013).

Study dosing and conversion and titration regimens for the TID and BID treatment groups in Part B, both guided by pre-Period 2 U-100, U-200, and/or U-300 insulin TDD (based on the highest TDD recorded in the 3 days prior to Period 2 which should be approximately unchanged from pre-Period 1) and baseline HbA1c (screening), and subsequent glucose monitoring, respectively, are based on literature expert reviews (Lane et al. 2009; Segal et al. 2010; Reutrakul, et al. 2012) and on the results from simulations performed using a systems physiology model of diabetes (in Physiolab®; de la Peña et al. 2014) based on data from previous PK/PD studies of

U-500R and U-100 human regular insulin (de la Peña et al. 2011; Studies F3Z-LC-IMAC and H7U-MC-IDBM).

9.4. Dose Conversion from Prestudy Insulin in Part B

Subjects will record their insulin doses throughout the study. Baseline U-100, U-200, and/or U-300 insulin TDD will be defined as the highest TDD recorded in the 3 days prior to Period 2. All U-100, U-200, and/or U-300 insulin therapy will be discontinued upon initiation of study drug, but permitted prestudy AHA therapy should continue to be taken at prestudy doses, except on clamp assessment days. For all subjects with HbA1c >8.0% at screening, initial U-500R TDD will be the same (in units) as U-100, U-200, and/or U-300 insulin TDD at screening.

For all subjects with baseline HbA1c ≤8.0% at screening, initial U-500R TDD dose will be reduced by 20% from the U-100, U-200, and/or U-300 insulin TDD at screening.

Initial TID dosing will use a 40:30:30 proportion of calculated U-500R TDD for the respective pre-meal doses at 07:00 hours, 12:00 hours, and 18:00 hours, approximately 30 minutes prior to the morning meal, midday meal, and evening meal, respectively.

Initial BID dosing will use a 60:40 proportion of calculated U-500R TDD for the respective pre-meal doses at 07:00 hours and 18:00 hours, approximately 30 minutes prior to the morning meal and evening meal, respectively.

During dose conversion, bolus doses will be rounded down to the nearest 5 U as was done in Study B5K-US-IBHC (Hood et al. 2015). If subjects are using 0.5-mL U-100 insulin syringes, this will be to the closest unit marking (0.01 mL) on the syringe; for those using 1.0-mL U-100 insulin syringes, this will be half way between unit markings (0.02 mL).

Subjects will record SMPG throughout Period 3. During telephone visits (conducted 2 days after the end of Period 2 at a minimum) the investigator or designee will titrate subjects' U-500R dose for each meal according to the algorithms presented in [Table IBHG.9.2](#).

During dose titration (as opposed to initial dosage conversion), conventional rounding to the nearest 5 U will be applied, so that, for instance, values between 120.1 and 122.4 would be rounded down to 120 U while values between 122.5 and 124.9 would be rounded up to 125 U.

Subjects should perform a 03:00 hours SMPG within 48 hours of any dose increase and should telephone the CRU the next morning if their 03:00 hours SMPG value is ≤70 mg/dL (≤3.9 mmol/L). The investigator may deviate from the algorithms, if deemed necessary, for the safety or well-being of the subject (for example due to illness, unusual SMPG patterns, or other safety concerns). Deviations from the algorithm should be discussed with Lilly, in advance if possible without compromising subject safety.

In the event of a subject reporting a severe hypoglycemic episode or any SMPG value is <50 mg/dL (<2.8 mmol/L), the investigator will make appropriate insulin adjustment per his/her judgment (this may be a 15% reduction in the appropriate U-500R mealtime dosage).

If a meal is skipped during the treatment period, the U-500R dose should be reduced by 50%.

Table IBHG.9.2. TID and BID Dosing Algorithms for U-500R Using Plasma-Equivalent Glucose Values

Algorithm	Insulin Dose to Adjust	Plasma-Equivalent Glucose Value	Value (mg/dL)	Action
TID Initial Dose Proportion 40:30:30	Pre-morning meal	Median pre-midday meal	≤70	Reduce dose by 10%
			71-130	No change in dose
			131-180	Increase dose by 5%
			181-220	Increase dose by 10%
			>220	Increase dose by 15%
	Pre-midday meal	Median pre-evening meal SMPG	≤70	Reduce dose by 10%
			71-130	No change in dose
			131-180	Increase dose by 5%
			181-220	Increase dose by 10%
			>220	Increase dose by 15%
BID Initial Dose Proportion 60:40	Pre-morning meal	Median pre-morning meal, median bedtime, or 03:00 hours SMPG	≤70	Reduce dose by 10%
			71-130	No change in dose
			131-180	Increase dose by 5%
			181-220	Increase dose by 10%
			>220	Increase dose by 15%
	Pre-evening meal	Median pre-morning meal, median bedtime, or 03:00 hours SMPG	≤70	Reduce dose by 10%
			71-130	No change in dose
			131-180	Increase dose by 5%
			181-220	Increase dose by 10%
			>220	Increase dose by 15%

Abbreviations: BID = twice daily; SMPG = self-monitored plasma glucose; TID = thrice daily.

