7.1.3. Part B (Study Period 3)

Following termination of the clamp procedure in Period 2, subjects will transition, as randomized, to TID or BID MDIs of U-500R. Human regular U-500 insulin will be self-administered by the subjects at home under telephone guidance from CRU staff during a telephone visit 2 to 3 days after the end of Period 2 (additional telephone or office visits may be added at the investigator's discretion). Initial U-500R doses will be based on each subject's insulin TDD prior to admission for Period 2, with titration for safety, if necessary, using the formulas given in Section 9.4. There will be 5 to 10 days between the end of Period 2 and the clamp in Period 3 (that is, dosing will begin on up to Day -10 and no later than Day -5 of Period 3) to allow steady state of the U-500R dosing regimen to be achieved. Mean self-monitored plasma glucose (SMPG) will be recorded from Day -5 until admission to the CRU.

Subjects will be admitted to the CRU on Day -1 of Period 3, prior to their pre-evening meal dose, which will be administered by CRU staff, and undergo fasting, PG stabilization, and a 24-hour euglycemic clamp as detailed in Section 7.1.2, with PK sampling as detailed in the Study Schedule ([Attachment 1](#)).

Following termination of the clamp procedure in Period 3 (Day 2), subjects will resume their prestudy insulin treatment regime. Discharge from the CRU will be subject to the same postclamp safety assessments as detailed in Section 7.1.2 and Section 10.4.1. Follow-up will occur 7 to 28 days after the end of Period 3 when safety procedures will be conducted and insulin use and dose will be recorded as detailed in the Study Schedule ([Attachment 1](#)).

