7.2. Discussion of Design and Control

In Part A of this study, a 2-period, randomized, crossover design has been chosen to allow each subject to act as his/her own control. Prestudy U-100, U-200, and/or U-300 insulin will be taken at the same dose and at approximately the same time each day prior to Period 1 and between Periods 1 and 2, and stopped at least 15 hours prior to U-500R bolus administration in Part A in order to reduce variation in insulin carryover (as the bioanalytical methodology is not specific to U-500R).

The use of a euglycemic clamp technique will provide data on the glucodynamic activity of U-500R. This is standard methodology routinely used to safely measure insulin action in clinical studies.

High-dose insulin-treated subjects with T2DM are representative of the population that is prescribed the U-500R formulation. An open-label design is considered appropriate as the PK/PD parameters being investigated in this study are objective endpoints.

Fasting and pre-meal plasma-equivalent glucose target ranges in Period 3 are 71 to 130 mg/dL (3.9 to 7.2 mmol/L), consistent with American Diabetes Association (ADA) standards of care (ADA 2012).

Recommended administration of U-500R bolus doses at least 30 minutes before meals by TID or BID dosing is based on USPI advice and PK/PD study results in obese, healthy subjects, which demonstrate both prandial and basal activity of U-500R (de la Peña et al. 2011).

The 5 to 10 days between Period 2 of Part A and the clamp procedure in Part B is expected to allow for subject recovery between clamps, for titration of doses, and for steady state to be achieved, given the findings of simulation modeling in which either TID or BID dosing steady state was predicted to be achieved by 24 hours (de la Peña et al. 2014).

8. Study Population

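### Protocol 9.4 defines one prestudy insulin TDD but converts from another, and nothing reconciles it with 7.1.3 for the Part B starting dose

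*Protocol*

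**What the plan says.** Four places in the protocol bear on the first U-500R dose in Part B.

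- **Section 9.4, definition.** "Baseline U-100, U-200, and/or U-300 insulin TDD will be defined as the highest TDD recorded in the 3 days prior to Period 2".
- **Section 9.4, conversion.** For screening HbA1c above 8.0%, "initial U-500R TDD will be the same (in units) as U-100, U-200, and/or U-300 insulin TDD at screening". For HbA1c of 8.0% or below, "initial U-500R TDD dose will be reduced by 20% from the U-100, U-200, and/or U-300 insulin TDD at screening". The result is split 40:30:30 (TID) or 60:40 (BID). On rounding: "During dose conversion, bolus doses will be rounded down to the nearest 5 U".
- **Section 7.1.3.** Initial doses rest on each subject's "insulin TDD prior to admission for Period 2, with titration for safety, if necessary, using the formulas given in Section 9.4".
- **Section 9.3.** The rationale says conversion is guided by the pre-Period 2 value, "based on the highest TDD recorded in the 3 days prior to Period 2 which should be approximately unchanged from pre-Period 1". The same sentence goes on to name the other inputs: "and baseline HbA1c (screening), and subsequent glucose monitoring". Here screening is the date for HbA1c only.

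The last paragraph of section 9.2 says Part B doses are determined as section 9.4 describes. On stability, section 7.2 asks that prestudy insulin be "taken at the same dose and at approximately the same time each day prior to Period 1 and between Periods 1 and 2", and section 9.2 asks for an approximately constant TDD throughout Part A.

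**The concern.** Section 9.4 sets up a defined term and then applies both of its conversion rules to a different quantity. The defined baseline TDD does no work in the section that defines it. Section 7.1.3 names the pre-Period 2 value and, in the same sentence, sends the reader to formulas that use the screening value. Site staff cannot satisfy both sections unless the two values happen to agree.

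The two quantities differ in kind as well as in date. The pre-Period 2 value is a 3-day maximum. The screening value has no stated rule: it could be the usual, the highest or a single-day dose.

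What is at stake is the instruction for the first U-500R doses that subjects give themselves at home. Two sites, or two staff members at one site, could read the protocol in good faith and enter different numbers.

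**Working it through.** The plan states no figure here that could be reproduced, so the check has three parts: the text side by side, the timing, and an illustration of size.

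**1. Which TDD each place uses**

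| Place | TDD named for the starting dose |
|---|---|
| 9.4, definition | Highest in the 3 days before Period 2 (not used afterwards) |
| 9.4, HbA1c above 8.0% | Screening |
| 9.4, HbA1c 8.0% or below | Screening, less 20% |
| 7.1.3 | Before admission for Period 2, by the 9.4 formulas |
| 9.3 (rationale) | Highest in the 3 days before Period 2 |
| 9.2 | None named; refers to 9.4 |

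Neither Attachment 1 nor the SAP gives an order of precedence.

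**2. How far apart the two readings can be**

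Inputs: screening up to 28 days before Day 1 of Period 1 (7.1.1); 7 to 21 days between the Period 1 and Period 2 boluses (7.1.2); admission on Day -1 (7.1.2).

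- Screening to the Period 2 bolus, at most: 28 + 21 = 49 days.
- Assume the 3 days are those before admission, Days -4 to -2. They lie 4 to 2 days before Day 1.
- Gap, at most: 49 - 4 = 45 to 49 - 2 = 47 days.

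This is the upper end under the nominal windows. It is shorter with an earlier Period 1 or a shorter washout. It can be longer if enrolment falls outside the 28-day window (8.1) or a clamp is repeated (10.2.3).

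**3. What a difference would do to the starting dose**

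The documents give no difference between the two TDDs, so both the 300 U and the percentage shifts below are assumptions.

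Formula from 9.4: starting total = sum over doses of (TDD × f × share), each dose rounded down to 5 U. Here f = 1 for HbA1c above 8.0% and 0.8 otherwise. Before rounding, the starting dose is proportional to the TDD used.

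For HbA1c above 8.0%, with 300 U at screening:

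| Assumed pre-Period 2 TDD | TID doses, total | BID doses, total |
|---|---|---|
| 270 U (-10%) | 108/81/81 → 105/80/80 = 265 | 162/108 → 160/105 = 265 |
| 300 U (no change) | 120/90/90 = 300 | 180/120 = 300 |
| 306 U (+2%) | 122.4/91.8/91.8 → 120/90/90 = 300 | 183.6/122.4 → 180/120 = 300 |
| 315 U (+5%) | 126/94.5/94.5 → 125/90/90 = 305 | 189/126 → 185/125 = 310 |
| 330 U (+10%) | 132/99/99 → 130/95/95 = 320 | 198/132 → 195/130 = 325 |

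The screening basis gives 300 U in every row. At +10% the two bases therefore differ by 320 - 300 = 20 U per day (TID) or 325 - 300 = 25 U per day (BID). At +2% rounding removes the difference.

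**The case against.** The strongest reply is that there is an operative rule. Section 9.2 says Part B doses are determined by 9.4, 7.1.3 points to the 9.4 formulas, and those formulas say screening. Section 9.3 is a rationale, not an instruction to the site. This is a fair point, and it rules out a reading that a reader might otherwise take: that the protocol names no basis for the starting dose. Several places do name one. The reply does not remove the conflict, because 9.4 contradicts its own definition and 7.1.3 names the other value in the sentence that refers to 9.4.

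The second reply is that the two values should hardly differ. Sections 7.2, 9.2 and 9.3 ask for the same or an approximately unchanged dose, and Attachment 1 has TDD recorded at screening and through Part A, so a discrepancy would be visible. This stands, and it limits the expected size. It does not make the values identical: approximate constancy leaves room for a difference, a 3-day maximum need not equal a screening value, and no text says what to do when they disagree.

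The third reply is that safeguards follow:

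- daily 4-point SMPG (7.1.4);
- a titration call 2 to 3 days after Period 2, with optional extra contacts (7.1.3, 9.4.1);
- investigator discretion (9.4);
- site contact for severe hypoglycemia or SMPG below 50 mg/dL (10.4.4).

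These also stand as limits on the consequence. They respond to glucose readings or events once dosing has begun, and none of them says which TDD to enter at the start.

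**Conclusion.** The inconsistency is real and lies in the current text: section 9.4 conflicts with its own definition and with 7.1.3, and nothing reconciles them. It should be fixed, but it is not a critical flaw.

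The documents give no size for the difference. Under compliance it should be small. The 20 to 25 U per day shown above rests wholly on an assumed 10% rise from an assumed 300 U. Totals of 300 U do appear in the worked examples of 9.4.1 and 9.4.2, but those are U-500R doses during Part B titration. They are not evidence about prestudy TDD.

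A reader might infer that the conflict produces materially wrong doses or biases the results. The documents do not support either inference:

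- No material dose difference is shown under protocol-compliant conduct.
- Part A, including its t_max analysis, and the sample size do not depend on this dose.
- Part B has no formal statistical analysis (11.2.4.2, 11.2.5.2), the conversion wording is the same for TID and BID, and doses are titrated after the start.

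**What to change.** Reconcile sections 7.1.3, 9.3 and 9.4 so that one TDD, with one date and one definition, drives both conversion sentences. If the screening value is retained, it needs a definition. If the pre-Period 2 value is retained, the conversion sentences need to use the term that 9.4 already defines. Which value sets the dose is for the sponsor's clinical team, and this review takes no position on it.

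The cost is a clarification or amendment of the protocol text. No new data are needed, because Attachment 1 already has TDD recorded at screening and through Part A.

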8.1.1. Inclusion Criteria

Subjects are eligible for enrollment in the study only if they meet all of the following criteria:

- [1] males or females with T2DM (World Health Organization [WHO] Classification of Diabetes [[Attachment 4](#)]; ADA, 2015).

- [1a] female subjects

are women of child-bearing potential who test negative for pregnancy at the time of screening based on a serum pregnancy test, and who agree to use a reliable method of birth control during the study

or

are women not of child-bearing potential due to surgical sterilization (at least 6 weeks after surgical bilateral oophorectomy with or without hysterectomy or at least 6 weeks after tubal ligation) confirmed by medical history, or menopause

menopausal women include women with either

1) spontaneous amenorrhea for at least 12 months, not induced by a medical condition such as anorexia nervosa and not taking medications during the amenorrhea that induced the amenorrhea (for example oral contraceptives, hormones, gonadotropin releasing hormone, anti-estrogens, selective estrogen receptor modulators, or chemotherapy)

or

2) spontaneous amenorrhea for 6 to 12 months and a follicle-stimulating hormone (FSH) level greater than 40 mIU/mL

- [2] are ≥ 18 to <75 years old at the time of screening
- [3] have a BMI of ≥ 27.0 kg/m² at screening
- [4] are current users of U-100, U-200, and/or U-300 insulin/analog as basal, premixed, and/or basal/bolus delivered with any injection device (pens and/or syringe/vial but excluding CSII/insulin pump use in the preceding 3 months), taking:
 - a TDD of ≥ 150 U
 - OR
 - at least one dose >100 U as part of an MDI regimen
- AND
- TDD ≤ 3.0 U/kg

[5] Concomitant AHA therapy may include:

- metformin (MET)
- dipeptidyl peptidase-4 inhibitors
- pioglitazone (doses ≤ 30 mg/day)
- GLP-1 receptor agonists
- sodium-glucose co-transporter-2 (SGLT2) inhibitors, except in combination with GLP-1 receptor agonists (see Exclusion Criterion [31] for excluded AHA therapy).

Subjects' AHA therapy must have been stable for ≥ 3 months (except for weekly GLP-1 receptor agonists which must have been stable for ≥ 4 months).

- [6] have HbA1c 7.5% to 11.5%, inclusive, as measured at screening
- [7] have venous access sufficient to allow for blood sampling and intravenous administration as per the protocol
- [8] are reliable and willing to make themselves available for the duration of the study and are willing and able to follow study procedures

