9.4.1. TID Treatment Group Titrations

Subjects in the TID treatment group will have their insulin doses adjusted at a telephone visit 2 to 3 days after the end of Period 2 (at a minimum, additional telephone or office visits may be added for safety as necessary) by the investigator or site designee according to the TID titration algorithm (Table IBHG.9.2).

The U-500R doses will be changed according to corresponding median plasma-equivalent glucose readings from the most recent 3 values at respective times (also see examples below) prior to the telephone or office visit or for any add-on telephone calls or office visits. If even

1 SMPG reading for a given time point is ≤ 70 mg/dL (≤ 3.9 mmol/L), no dosage increase will be applied to the corresponding dose. These adjustments will be applied only to the 2 of the 3 doses (pre-morning meal, pre-midday meal, pre-evening meal) that most need adjustment (that is, the ones with the most out-of-range corresponding median plasma-equivalent glucose readings) at each study visit/interaction.

For subjects receiving U-500R TID, median pre-morning meal and bedtime SMPG values and 03:00 hours SMPG values (if performed) will inform adjustment of the pre-evening meal U-500R insulin dose. When these 3 sets of values provide conflicting guidance, the investigator should base the dose adjustment on the lowest of these results, and prioritize adjustments for hypoglycemic readings ≤ 70 mg/dL (≤ 3.9 mmol/L) over dosage increases.

In all instances, the 10% dosage reduction for values ≤ 70 mg/dL (≤ 3.9 mmol/L) and negation of respective dosage increases for single pre-meal or bedtime hypoglycemic readings should be prioritized over other titration options.

Example 1

A subject assigned to the TID treatment group is taking 300 U TDD with a pre-morning meal dose of 120 U, pre-midday meal dose of 90 U and a pre-evening meal dose of 90 U.

Over the last 3 days, the subject's SMPG values were:

Date	Day 1	Day 2	Day 3
SMPG pre-morning meal, mg/dL (mmol/L)	102 (5.7)	110 (6.1)	135 (7.5)
SMPG pre-midday meal, mg/dL (mmol/L)	163 (9.1)	180 (10.0)	200 (11.1)
SMPG pre-evening meal, mg/dL (mmol/L)	240 (13.3)	221 (12.3)	238 (13.2)
SMPG at bedtime, mg/dL (mmol/L)	130 (7.2)	160 (8.9)	125 (6.9)
SMPG at 03:00 hours, mg/dL (mmol/L)			92 (5.1)

Abbreviation: SMPG = self-monitored plasma glucose.

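### Rounding titrated doses to the nearest 5 U cancels the ordered 10% hypoglycaemia cut at doses of 25 U or less; a 5-U minimum cut closes this rare gap

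*Protocol*

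**What the plan says.** Protocol Section 9.4 uses two rounding rules. At initial conversion each dose is rounded down to a multiple of 5 U. Afterwards, "During dose titration (as opposed to initial dosage conversion), conventional rounding to the nearest 5 U will be applied". The midpoint goes up, because "values between 122.5 and 124.9 would be rounded up to 125 U". On the 0.5-mL syringe, rounding to 5 U is explained this way: "this will be to the closest unit marking (0.01 mL) on the syringe".

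In Table IBHG.9.2 the action for a value of 70 mg/dL or lower is "Reduce dose by 10" percent, for both regimens. Section 9.4.1 ranks that action above the other titration options: "In all instances, the 10% dosage reduction for values" at or below 70 mg/dL comes first. Section 9.4.2 says the same for BID.

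Two provisions allow judgment. Section 9.4 states: "The investigator may deviate from the algorithms, if deemed necessary, for the safety or well-being of the subject". It asks that such deviations be discussed with the sponsor, in advance where that is safe. For severe hypoglycaemia or a reading below 50 mg/dL the investigator decides, and "this may be a 15% reduction in the appropriate U-500R mealtime dosage".

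No minimum step is given, and nothing covers a reduction that rounds back to the dose already being taken.

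**The concern.** A 5-U grid cannot express 10% of a small dose. Where 10% of the dose is 2.5 U or less, the reduced value rounds back to where it started, and the row for values of 70 mg/dL or lower gives the same dose as the no-change row for 71 to 130 mg/dL. The step that the protocol places ahead of all others then has no effect.

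The worked examples do not show this, because none uses a dose below 60 U. Titration may be done by a site designee, who could reasonably apply the table and the rounding rule literally. Readings from 50 to 70 mg/dL have no specific rule other than the table. A subject with repeated low values could therefore stay on the same dose although the algorithm had ordered a cut.

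**Working it through.** **Inputs (all from the protocol).** Titration rounding to the nearest 5 U with midpoints up, conversion rounding down to 5 U, TID split 40:30:30, BID split 60:40, and a 20% starting reduction if HbA1c is 8.0% or lower (Section 9.4). A 10% cut at 70 mg/dL or lower (Table IBHG.9.2). HbA1c 7.5% to 11.5%, and entry with either a total daily dose (TDD) of at least 150 U or "at least one dose >100 U as part of an MDI regimen" (Section 8.1.1).

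**Formulas.**
- Titrated dose = 5 × floor(dose × (1 + change)/5 + 0.5)
- Starting dose = 5 × floor(TDD × k × share/5), with k = 0.8 if HbA1c ≤8.0% and k = 1 otherwise

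**Step 1: the plan's own examples.** The titration formula reproduces every worked dose change in Sections 9.4.1 and 9.4.2. For instance, 165 × 0.90 = 148.5 → 150; 60 × 0.90 = 54 → 55; 90 × 0.90 = 81 → 80; 110 × 0.90 = 99 → 100. The rounding illustrations in Section 9.4 (120.1 and 122.4 → 120; 122.5 and 124.9 → 125) also agree.

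**Step 2: the 10% cut at small doses.**

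| Current dose (U) | × 0.90 | Rounded | Actual cut |
|---|---|---|---|
| 20 | 18.0 | 20 | 0 |
| 25 | 22.5 | 25 | 0 |
| 30 | 27.0 | 25 | 5 U (16.7%) |
| 35 | 31.5 | 30 | 5 U (14.3%) |
| 45 | 40.5 | 40 | 5 U (11.1%) |
| 60 | 54.0 | 55 | 5 U (8.3%) |
| 75 | 67.5 | 70 | 5 U (6.7%) |

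The cut is exactly 5 U at every dose from 30 to 75 U and zero at 25 U and below, so the 25-U threshold is exact. The amount not removed is 2.5 U at 25 U and 2 U at 20 U.

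**Step 3: starting doses of 25 U or less.** The single-dose entry route requires a TDD above 100 U. For TID with HbA1c ≤8.0%, the midday and evening shares are 0.8 × 0.30 = 0.24 of TDD:
- TDD 101: 24.24 → 20 U; TDD 104: 24.96 → 20 U
- TDD 105: 25.2 → 25 U; TDD 124: 29.76 → 25 U
- TDD 125: 30.0 → 30 U

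For TID with HbA1c >8.0%, the smallest share at TDD 101 is 0.30 × 101 = 30.3 → 30 U. For BID with HbA1c ≤8.0% it is 0.8 × 0.40 × 101 = 32.32 → 30 U, and for BID with HbA1c >8.0% it is 0.40 × 101 = 40.4 → 40 U. Only TID with HbA1c ≤8.0% can start at 25 U or less.

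**Step 4: reaching 25 U after earlier cuts.** A 30-U dose needs one cut (30 → 25) and a 35-U dose needs two (35 → 30 → 25).
- TID, HbA1c ≤8.0%: one cut if 0.24 × TDD < 35, that is TDD up to 145 U; two if 0.24 × TDD < 40, up to 166 U.
- TID, HbA1c >8.0%: one cut if 0.30 × TDD < 35, up to 116 U; two if 0.30 × TDD < 40, up to 133 U.
- BID evening dose, HbA1c ≤8.0%: one cut if 0.32 × TDD < 35, up to 109 U.

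The lowest starting dose for a subject entering with TDD of at least 150 U is 0.24 × 150 = 36 → 35 U, so that route needs two earlier cuts.

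**Step 5: the proposed minimum cut.** 25 → 20 (20%) and 20 → 15 (25%). The optional 15% cut for readings below 50 mg/dL already gives these doses: 25 × 0.85 = 21.25 → 20 and 20 × 0.85 = 17 → 15.

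**The case against.** The protocol contains no miscalculation: every example is right, and coarse rounding was a deliberate choice. The priority wording ranks competing actions and does not promise a minimum number of units. A low reading still blocks an increase at 25 U, so the ranking works as written.

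The affected group is also very small. Entry through a single dose above 100 U requires a multiple-injection regimen, so a TDD of 101 to 104 U leaves less than 4 U for all other insulin, and 105 to 124 U leaves less than 24 U. The subject must also be assigned to TID and have HbA1c no higher than 8.0%. Unless a single 03:00 value triggers the cut, at least two of the last three readings at one time point must be low. Only one titration call is mandatory in the 5 to 10 days, so repeated cuts are uncommon. The investigator may deviate for safety, contacts can be added, and subjects are told to treat any reading of 70 mg/dL or lower. It is plausible that no subject would be affected.

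The points on rarity and small risk stand. The override does not settle the matter, because the protocol treats its use as a deviation to be discussed with the sponsor. At these doses, delivering the reduction that the table orders would itself be a deviation. The narrower reading of the priority wording is fair, but it does not explain why a row ordering a reduction should leave the dose unchanged.

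**Conclusion.** The concern holds, as an optional correction. Taken together, the table and the rounding rule turn an ordered hypoglycaemia reduction into no change at 25 U or less, and the entry criteria permit such doses. Part A is not touched, and Part B is summarised without formal analysis.

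The arithmetic is exact. Reach is given for whole-unit TDDs and assumes that the TDD used for conversion is the one on which the subject qualified. The documents give no distribution of TDD, so the number of affected subjects cannot be estimated.

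The same rounding makes 5% increases ineffective at 45 U or less (45 × 1.05 = 47.25 → 45). That errs on the cautious side by about 2 U and needs no change.

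**What to change.** Add to protocol Section 9.4, after the titration rounding rule:

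> *A reduction ordered for a value of 70 mg/dL or lower lowers the dose by at least 5 U (one marking on the 0.5-mL syringe).*

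Add one worked example: current dose 25 U, median 66 mg/dL, calculated 22.5 U, give 20 U. Leave the rounding of increases as it is.

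One marking is 0.01 mL × 500 U/mL = 5 U, the smallest step the scheme allows. The larger percentage cuts at 20 and 25 U continue the existing pattern, since 30 U already falls by 16.7%. At 20 and 25 U the response to a value of 70 mg/dL or lower would equal the optional 15% response to a reading below 50 mg/dL. Rounding already makes the two equal from 30 to 50 U (30: 27 and 25.5 → 25; 40: 36 and 34 → 35; 50: 45 and 42.5 → 45).

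The drafting cost is one sentence and one example. If the sponsor regards a changed dosing rule as a major modification under Section 10.6, it also needs a protocol amendment and could be included in the next one.
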